5.1.2 Exclusion Criteria

Prior Therapy

- ____ 1. Anti-PD-1, anti-PD-L1, or anti-PD-L2 agents
- ____ 2. Prior radiation therapy within the field of the target lesion that in the opinion of the treating radiation oncologist would preclude further palliative radiation to a dose of 30 Gy.
- ____ 3. Anti-cancer monoclonal antibody (mAb) within 4 weeks prior to study Day 1 or who has not recovered (i.e., \leq Grade 1 or at baseline) from adverse events due to agents administered more than 4 weeks earlier.
- ____ 4. Chemotherapy, targeted small molecule therapy, or radiation therapy within 2 weeks prior to study Day 1 or who has not recovered (i.e., \leq Grade 1 or at baseline) from adverse events due to a previously administered agent.
 - Note: Subjects with \leq Grade 2 neuropathy are an exception to this criterion and may qualify for the study.
 - Note: If subject received major surgery, they must have recovered adequately from the toxicity and/or complications from the intervention prior to starting therapy.
- ____ 5. Live vaccine within 30 days of planned start of study therapy.
 - Note: Seasonal influenza vaccines for injection are generally inactivated flu vaccines and are allowed; however intranasal influenza vaccines (e.g., Flu-Mist®) are live attenuated vaccines, and are not allowed.
- ____ 6. Immunosuppressive therapy within 7 days prior to the first dose of trial treatment.

7. Investigational device within 4 weeks of the first dose of treatment

Concomitant Therapy

8. Currently receiving an investigational agent

9. About to undergo palliative radiation for a symptomatic CNS metastasis

10. Systemic steroid therapy

Other Illnesses and Conditions

11. Hypersensitivity to pembrolizumab or any of its excipients

12. Diagnosis of immunodeficiency

13. Active autoimmune disease that has required systemic treatment in the past 2 years (i.e. with use of disease modifying agents, corticosteroids or immunosuppressive drugs).

- Replacement therapy (e.g. thyroxine, insulin, or physiologic corticosteroid replacement therapy for adrenal or pituitary insufficiency, etc.) is not considered a form of systemic treatment.

14. Known history of, or any evidence of active, non-infectious pneumonitis.

15. Current active infection requiring systemic therapy

16. Known history of active TB, HIV 1/2, Hepatitis B or Hepatitis C

17. Known additional malignancy that is progressing or requires active treatment.

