j.	Tumor biopsies will be performed prior to cycle 1/day 1, and at 21 days (± 3 days) after completion of palliative radiotherapy. Biopsies will be performed of metastatic sites amenable to access by CT or ultrasound-guidance. Malignant ascites accessible by ultrasound guidance will also be eligible as tumor biopsy specimens. For patients receiving RT to a metastatic site and only the primary tumor is accessible to biopsy, these will be obtained by endoscopy.													
k.	Blood/stool/oral swab collection for correlative studies will be collected at screening assessment, at 21 days (± 3 days) after completion of palliative radiotherapy, at timepoint of first progression by RECIST (if applicable and continued on protocol therapy), and at end of treatment.													

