7.1.2.7 Tumor Tissue Collection and Correlative Studies Blood/Stool/Oral Swab Sampling

7.1.2.7.1 Analysis of pre- and post-treatment tumor biopsies

Tumor biopsies will be performed during the Screening Phase and 21 days after completion of palliative radiotherapy. CT or ultrasound-guided biopsies will utilize 20-gauge core biopsy needles. As such tissue samples will be composed of both tumor cells and associated tumor stroma. Fresh tumor samples will be immediately delivered to the laboratory of [name] for both ex vivo tumor/immune/stromal cell culture and expansion as well as histologic analyses. Patients with fresh malignant ascites collected by ultrasound guidance will also be immediately delivered to the lab for ex vivo tumor/immune/stromal cell culture and expansion alone.

[name] lab will utilize quantitative spatial image analysis to examine changes in tumor cell-stromal interactions including CD4, CD8, Treg, and MDSC populations pre- and post-therapy.

PD-L1 expression within the tumor, on cancer cells and stromal cells, will be analyzed by immunohistochemistry (IHC) locally in [name] lab, as well as centrally through QualTek Laboratories. PD-1 expression on tumor infiltrating T cells will be analyzed by a combination of IHC and flow cytometry. Immune cell populations will be further analyzed via high dimensional flow cytometry to measure levels of Tregs and MDSCs. [name] lab will also pursue multi-color IHC to determine influences of pembrolizumab+RT treatment on the magnitude and proximity of CD8 T cells to cancer cells within the tumor. Changes in the diversity of the T cell repertoire in both PD-1 positive and PD-1 negative T cell populations following pembrolizumab+RT treatment will be analyzed via deep sequencing of the TCR V β CDR3 region. Such changes in T cell repertoire can be suggestive of potential epitope spreading for anti-tumor antigens and reversal of tumor antigen-specific T cell anergy. Genomic analyses utilizing City of Hope's Integrative Genomics Core will also be performed on the corresponding cancer/stromal/immune cell populations via total RNA-seq for coding and non-coding RNAs (including miRNAs).

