7.1.2.7.2 Correlative Studies Blood Sampling

Circulating T cell, Tregs, and MDSC Isolation and Characterization

Blood Sample Collection

Blood samples will be collected from an indwelling venous catheter or by venipuncture into three 7 mL green-top tubes (sodium or lithium heparin) at three timepoints: (1) Screening visit, (2) 21 days after completion of palliative radiotherapy, and (3) at the time of first progression by traditional RECIST1.1 (to capture potential pseudoprogression and only applicable for patients continued on treatment beyond progression), and at end of treatment. To prevent blood clotting, tubes will be inverted several times and then immediately placed on ice for transportation to the CICSL (Clinical Immunobiology Correlative Studies) processing laboratory. The whole blood should be processed within 4 hours of collection. While awaiting processing, the blood should be kept on a rocker set at low speed to mimic circulation and avoid clot formation.

Sample Processing in CICSL

Plasma

- For plasma preparation, anti-coagulated whole blood (two 7 mL green-top tubes) will be processed by centrifugation for 10 minutes at 1000 x g at 4°C. The resulting upper plasma layer from each tube will be drawn up sequentially into a sterile 5 mL syringe and pushed through a sterile 0.2/0.8 micron disposable filter (PALL Acrodisc PF, Cat. 4658). The filtered plasma will then be transferred in 500 µL aliquots into multiple appropriately-labeled Starstedt microfuge tubes (Starstedt Cat 72.692.005). To one aliquot, add 0.5 mL glycerol/0.02% sodium azide solution to dilute the plasma 50/50 v/v. **Keep the diluted plasma sample at -20°C and do not freeze.** All the remaining plasma aliquots will be stored frozen at -80°C until ready for testing.

PBMCs

- Any blood remaining in the two 7 mL green-top tubes used to prepare plasma above will be diluted 1:1 with Hank's Balanced Salt Solution ("HBSS", Irvine Scientific, Cat. 9228 or equivalent) and combined with the whole blood from the unused green-top tube in a sterile 50 ml conical centrifuge tube. Peripheral blood mononuclear cells

(PBMC) will then be isolated from the combined whole blood sample by Ficoll-gradient separation as described below;

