PD-1 expression on circulating PBMC T cells will be analyzed by flow cytometry. Immune cell populations will be further analyzed via high dimensional flow cytometry to measure levels of Tregs and MDSCs, which will allow for calculating the ratio of effector T cells to Tregs and MDSCs, respectively. Ex vivo isolated T cells will also be analyzed for proliferative

capacity (CFSE dilution) and cytokine production (IFN- γ and IL-17) after stimulation with anti-CD3 and/or PMA and Ionomycin.

Serum Circulating miRNA Profiling

20 mL of whole blood will be collected from each patient into 2 Vacutainer red top tubes (no additive) at three timepoints: (1) Screening visit, (2) 21 days after completion of palliative radiotherapy, and (3) at the time of first progression by traditional RECIST1.1 (to capture potential pseudoprogression and only applicable for patients continued on treatment beyond progression), and at end of treatment. Blood will be allowed to clot on ice for 15-20 min, and then centrifuged at 1900g (3000 rpm) for 10 minutes at 4°C using a swinging bucket rotor. The upper (yellow) serum phase will then be transferred to four separate labeled cryovials without disturbing the intermediate buffy coat layer. The cryovials will be placed on ice, and then delivered immediately for storage in the Fox North Building, Room N2002, freezer EFRU385. Serum samples will be stored frozen at -80 °C until time of analysis.

Total RNA will be extracted using Trizol within the Integrative Genomics Core at City of Hope for miRNA-seq. Sequence reads that match human miRNAs in Sanger mirBase will be calculated and analyzed. Circulating whole genome miRNA signatures will be compared to miRNAs sequenced from total RNA-seq from the corresponding tumor biopsy timepoints to aid in biomarker discovery of serum miRNAs that may predict for immunotherapy response or resistance. miR-23a will be of particular interest given its description as a gastric cancer oncomir and function as a repressor of T cell cytotoxicity in preclinical miRNA screens.^{14,15} miR-34a and miR-200 will be other miRNAs of interest to measure given reporting of their ability to suppress PD-L1 expression in other experimental systems.^{16,17}

Germline miRNA biomarker analysis

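### Washouts run to Day 1, not to the baseline sample, so a compliant baseline biopsy or blood draw can precede the end of washout, and Section 9.1 has no analysis of that interval

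*Combined protocol and SAP*

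**What the plan says.** **Baseline samples.** Section 6.1 footnote j says "Tumor biopsies will be performed prior to cycle 1/day 1", and Section 7.1.2.7.1 says "Tumor biopsies will be performed during the Screening Phase and 21 days after completion of palliative radiotherapy". For blood, footnote k says "Blood/stool/oral swab collection for correlative studies will be collected at screening assessment". Section 7.1.2.7.2 repeats the screening visit for the immunophenotyping tubes ("three 7 mL green-top tubes (sodium or lithium heparin) at three timepoints: (1) Screening visit, (2) 21 days after completion of palliative radiotherapy") and for the serum miRNA tubes ("2 Vacutainer red top tubes (no additive) at three timepoints: (1) Screening visit"). The calendar gives the screening window as days -21 to -1.

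**Washouts.** Section 5.1.2 excludes "Chemotherapy, targeted small molecule therapy, or radiation therapy within 2 weeks prior to study Day 1" and "Anti-cancer monoclonal antibody (mAb) within 4 weeks prior to study Day 1". Both criteria also exclude patients whose adverse events from earlier agents have not settled to Grade 1 or baseline.

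**Other relevant rules.** Section 5.3.2 bars chemotherapy, biological therapy and most other listed treatments from the start of Screening. Exclusion 19 lets the investigator exclude a patient whose therapy might confound the results. Section 5.1.1 allows any number of prior lines, or none. Table 5 in Section 7.1.3 lists correlative blood, and the text below it sets a 10-day limit on screening laboratory tests.

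**Analysis.** Section 9.1 uses each patient as their own control in a one-sided paired t-test with 14 patients. It does not use time since last therapy.

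**The concern.** The primary endpoint is a change in immune-cell populations, and the baseline is the only comparator. If the baseline is taken soon after chemotherapy or an antibody, and the second sample several weeks later, any change due to coming off that therapy forms part of the paired difference. With no comparison arm it cannot be separated from the effect of pembrolizumab plus radiotherapy. Patients may be heavily pretreated or treatment-naive, so the interval may differ widely among only 14 patients. Section 9.1 makes a positive biological signal part of the case for the combination, so a drift in either direction could mislead that judgement.

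**Working it through.** **1. The plan's own figure.** Inputs from Section 9.1: n = 14 pairs, effect size 0.71 (mean difference divided by its SD), one-sided alpha 0.05. Power = P(T > t(0.95, 13)), where T is noncentral t with 13 df and noncentrality 0.71 × √14. The result is 80.8%, against 80% stated. The sample-size figure is right.

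**2. Shortest compliant gap to the baseline sample.** Day -14 is two weeks before Day 1, so the last permitted chemotherapy day is -15; for an antibody it is -29. Boundary counting may move these by a day.
- Chemotherapy: dose on day -15, Screening and sample on day -14. Gap 15 - 14 = 1 day. This also satisfies Section 5.3.2.
- Antibody: dose on day -29, sample on day -21. Gap 29 - 21 = 8 days.
- Blood, if the 10-day rule applies: earliest draw on day -10. Gaps 15 - 10 = 5 days and 29 - 10 = 19 days.

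**3. Time of the second sample.** Ten weekday fractions from Day 1 end on day 12 (Monday start) or day 14 (Tuesday to Friday start). Adding 21 ± 3 days gives day 30 to 36 or day 32 to 38, without holidays or delays. Footnote e allows radiotherapy to run later.

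**4. What a drift would do.** The drift sizes are assumptions; the documents give none. With no treatment effect, the same noncentral t calculation applies with the drift in place of 0.71. Where only some patients drift, simulation was used (14 normal differences, SD 1).

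| Assumed drift, favourable direction | Chance of a positive test (nominal 5%) |
|---|---|
| 0.1 SD, all 14 pairs | 9.9% |
| 0.2 SD, all 14 pairs | 17.5% |
| 0.3 / 0.5 SD, 3 of 14 | 7.6% / 9.7% |
| 0.3 / 0.5 SD, 7 of 14 | 12.9% / 20.9% |

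The all-14 rows assume that no treatment-naive patient enrols. For an unfavourable drift of 0.1 or 0.2 SD, the net effect is 0.71 - 0.1 = 0.61 or 0.71 - 0.2 = 0.51, and power falls from 81% to 70% or 56%. With no drift nothing changes.

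**5. What a restricted analysis can show.** The 95% half-width in SD units is t(0.975, n-1)/√n. The subset sizes are assumed.

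| Pairs | Half-width | Power at 0.71 |
|---|---|---|
| 14 | 0.58 | 81% |
| 10 | 0.72 | 67% |
| 8 | 0.84 | 57% |
| 5 | 2.776/√5 = 1.24 | not calculated |

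**The case against.** Several provisions narrow the gap. Section 5.3.2 stops dosing once Screening starts, the recovery rule removes patients with unresolved toxicity, and exclusion 19 addresses confounding by therapy directly. The antibody washout and the screening window together imply about 8 days before any sample. The 10-day rule may govern the blood, although the calendar does not attach its 10-day footnote to the correlative row. All of this stands and limits the point. None of it ties the sample to the last dose: recovery from adverse events is not a statement about immune-cell levels, and exclusion 19 is discretionary.

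Three stronger readings are tempting and are not supported.
- A reader might infer that Sections 5.1.2 and 5.3.2 contradict each other on chemotherapy between days -21 and -15. They do not: one is an exclusion, the other a further prohibition, and a patient can meet both by satisfying the stricter.
- A reader might infer that nobody could later judge whether timing mattered. Last-dose dates must be known to verify eligibility, and Sections 7.1.1.5 and 11.1.3.2 collect prior cancer treatment. The data should exist; the pre-specified use of them does not.
- A reader might infer that the primary result will be biased. The documents do not show that drift occurs, and the rates above would follow from any bias of the same size.

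It is also fair that the change below leaves the biopsy, which is central to the primary endpoint, where it is.

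**Conclusion.** The point holds as a cheap improvement, not as an error; the power statement is correct. The washouts end at Day 1, the baseline samples need not follow them, and Section 9.1 has no analysis of the interval. The shortest compliant gaps are about 1 day after chemotherapy and 8 days after an antibody (about 5 and 19 days for blood on the 10-day reading). These are extreme cases, and the documents do not say how many patients would come near them. Treatment-naive patients are unaffected. Whether leaving prior therapy changes these cell populations, by how much and in which direction, is unknown, so the false-positive and power figures only illustrate sensitivity to assumed drift.

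**What to change.** 1. In Section 6.1 footnote k and the immunophenotyping part of Section 7.1.2.7.2, draw the baseline green-top blood for circulating T cells, Tregs and MDSCs on C1D1, before the first fraction and the infusion. It then follows the full Section 5.1.2 washout. Section 5.2.2 already puts Day 1 procedures before treatment, and a CBC is drawn that day. Align Table 5 and the 10-day wording in Section 7.1.3. Leave the serum miRNA draw at screening, because it is compared with "miRNAs sequenced from total RNA-seq from the corresponding tumor biopsy timepoints". Leave stool, oral swabs and biopsy timing unchanged.
2. From the last-dose dates needed for eligibility (Sections 7.1.1.5 and 11.1.3.2), derive days from last therapy to each baseline sample. Do not rely on the prior-medication list in Section 7.1.1.4, which leaves out treatment for the study disease.
3. Pre-specify in Section 9.1 a supportive estimate of the paired difference with a 95% confidence interval, in treatment-naive patients and those whose baseline sample came after the Section 5.1.2 intervals. Say that these intervals are a convenient cut-off, not evidence of immune recovery. Add a plot of paired difference against days since last therapy. With the blood moved, this bears mainly on the biopsy.

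The cost is wording in the calendar, Section 7.1.2.7.2, Section 7.1.3 and Section 9.1; no patient, biopsy or visit is added. Baseline research blood is split into two draws, and circulating and tumor baselines may fall on different days. The supportive set will be small, with a half-width of about 0.72 SD with 10 pairs and 1.24 SD with 5, and it cannot exclude drift. The plan should say so.

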6.2 Second Course Phase

Trial Period:	Treatment Cycles					End of Treatment	Post-Treatment
	C1/D1	C2/D1	C3/D1	C4D1	C5D1		
Treatment Cycle:					C6+D1 ^a	Last Dose	Safety Follow-up
Scheduling Window (Days):			± 3	± 3	± 3	At time of Discon	Follow Up Visits ^b
Administrative Procedures							
Inclusion/Exclusion Criteria	X						
Prior and Concomitant Medication Review	X	X	X	X	X	X	X
Post-study anticancer therapy status							X
Survival Status							X
Clinical Procedures/Assessments							
Review Adverse Events	X	X	X	X	X	X	X
Full Physical Examination	X					X	
Directed Physical Examination		X	X	X	X	X	X
Vital Signs and Weight	X	X	X	X	X	X	X
ECOG Performance Status	X	X	X	X	X	X	X
Pembrolizumab	X	X	X	X	X	X	
Laboratory Procedures/Assessments							
Pregnancy Test – Urine or Serum β-HCG	X						X
PT/INR and aPTT	X						
CBC with Differential	X	X	X	X	X	X	X

Trial Period:	Treatment Cycles						End of Treat- ment	Post-Treatment		
	C1/D1	C2/D1	C3/D1	C4D1	C5D1	C6+D1 ^a		Last Dose	Safety Follow- up	Follow Up Visits ^b
Treatment Cycle:										
Scheduling Window (Days):										
Comprehensive Serum Chemistry Panel	X	X	X	X	X	X	At time of Discon	30 days post discon	Every 6 weeks post discon	Every 12 weeks
Urinalysis	X						X	X		
T3, FT4 and TSH ^d	X			X		X				
Serum carcinoembryonic antigen (CEA) ^e	X		X		X	X	X	X		
Efficacy Measurements										
Tumor Imaging ^f			X		X	X	X	X	X ^g	

a. Patients will continue pembrolizumab for a maximum of 17 cycles for second course of therapy if no evidence of disease progression or intolerable toxicity.

b. In patients who discontinue study therapy without documented disease progression, every effort should be made to continue monitoring disease status by radiologic imaging every 6 weeks (± 7 days) until 1) the start of new anti-cancer treatment, 2) disease progression on imaging, 3) death, or 4) the end of the study, whichever occurs first.

c. After the start of new anti-cancer treatment or documented disease progression by imaging, the patient should be contacted by telephone every 12 weeks to assess for survival status.

d. Thyroid function tests should be collected at C1/D1 and every 6 weeks in concordance with day 1 of odd-numbered cycles.

e. Serum CEA should be collected at C1D1 and every 6 weeks in concordance with day 1 of odd-numbered cycles.

f. Tumor imaging should be performed every 6 weeks through the first 6 cycles, then subsequently performed every 9 weeks thereafter. For patients who complete 35 cycles of second course therapy or 2 years of follow up without evidence of progression, scans can be spaced out to every 12-24 weeks at the discretion of the treating physician. The exception will be patients who demonstrate PD, PR, or CR by RECIST 1.1, in which event the next imaging will be performed at 6 weeks for confirmation. Refer to Section 7.1.2.6.2 for details.

7.0 TRIAL PROCEDURES

7.1 Trial Procedures

The Study Calendar - [Section 6.0](#) summarizes the trial procedures to be performed at each visit. Individual trial procedures are described in detail below. It may be necessary to perform these procedures at unscheduled time points if deemed clinically necessary by the investigator.

Furthermore, additional evaluations/testing may be deemed necessary by the Sponsor and/or Merck for reasons related to subject safety. In some cases, such evaluation/testing may be potentially sensitive in nature (e.g., HIV, Hepatitis C, etc.), and thus local regulations may require that additional informed consent be obtained from the subject. In these cases, such evaluations/testing will be performed in accordance with those regulations.

7.1.1 Administrative Procedures

7.1.1.1 Informed Consent

The Investigator must obtain documented consent from each potential subject prior to participating in the clinical trial. Consent must be documented by the subject's dated signature or by the subject's legally acceptable representative's dated signature on a consent form along with the dated signature of the person conducting the consent discussion.

A copy of the signed and dated consent form should be given to the subject before participation in the trial.

The initial informed consent form, any subsequent revised written informed consent form and any written information provided to the subject must receive the IRB's approval/favorable opinion in advance of use. The subject or his/her legally acceptable representative should be informed in a timely manner if new information becomes available that may be relevant to the subject's willingness to continue participation in the trial. The communication of this information will be provided and documented via a revised consent form or addendum to the original consent form that captures the subject's dated signature or by the subject's legally acceptable representative's dated signature.

Specifics about a trial and the trial population will be added to the consent form template at the protocol level.

The informed consent will adhere to IRB requirements, applicable laws and regulations and COH requirements.

7.1.1.2 Inclusion/Exclusion Criteria

All inclusion and exclusion criteria will be reviewed by the investigator or qualified designee to ensure that the subject qualifies for the trial.

